7.2.1 Screening

After written informed consent has been obtained, subjects will be screened in order to assess eligibility for study participation. All screening procedures must be performed within 14 days prior to start of investigational product administration, unless otherwise noted. The ICF may be signed earlier than 14 days prior to start of investigational product in case of washout times that have to be observed to meet eligibility criteria. Re-consent is necessary if the date of consent is longer than 14 days prior to the start of the first dose of AMG 427.

Subjects who meet the inclusion and exclusion criteria will be eligible to be enrolled in the study. Subjects who do not meet the eligibility criteria within the 14-day screening period will not be eligible for enrollment. Subjects who are deemed ineligible will be documented as screen failures.

Laboratory assessments used to determine subject eligibility may be repeated once for confirmation (up to a total of 2 times during the 14-day screening period) if necessary

before the subject is considered a screen failure. If any assessments are repeated during the screening period, the value that is closest to the enrollment date will apply for the determination of eligibility.

The following procedures are to be completed during the screening period at the time points designated in the Schedules of Assessments ([Table 10](#) to [Table 23](#)).

Assessments that were performed as standard of care prior to signature of informed consent but within 14 days prior to start of treatment with AMG 427 can be used as screening assessments and do not need to be repeated to confirm subject eligibility.

Hepatitis serology does not need to be repeated to determine eligibility if it was performed within 6 weeks prior to start of treatment with AMG 427.

- Confirmation that the ICF has been signed
- Demographic data including sex, age, race, and ethnicity will be collected in order to study their possible association with subject safety
- Clinical evaluation
 - Physical examination as per standard of care (including medical/surgical history). Physical examination findings should be recorded on the appropriate eCRF.
 - ECOG performance status
 - Height and weight
- Vital signs (ie, blood pressure, heart rate, respiratory rate, temperature)
- Pulse oximetry
- ECG triplicate measurements (2 sets of triplicates)
- Laboratory assessments: hematology, chemistry, coagulation, urinalysis, serum pregnancy test (females only), and hepatitis serology
- Estimated glomerular filtration rate (eGFR)
- Bone marrow assessments
- Serious adverse event reporting
- Documentation of concomitant and rescue medications.

Re-screening:

A subject may be rescreened up to 3 additional times during the study at the discretion of the investigator. The subject must be re-consented if a re-screening attempt occurs outside the 14-day screening period.

Re-screened subjects must be documented as screen failed in the subject's medical record and subsequently documented as re-screened. Subjects will retain the same subject identification number assigned at the time of initial screening. Once the subject

is recorded as re-screened, a new 14-day screening window will begin. The following assessments do not have to be repeated during re-screening if they were performed as standard of care or during the initial screening attempt within the time frames specified below:

- Hepatitis serology does not need to be repeated if it was performed within 6 weeks prior to start of treatment with AMG 427
- Bone marrow assessments (except molecular panel, see last bullet) do not need to be repeated if done within 4 weeks prior to start of treatment with AMG 427 as long as subject did not receive any anti-leukemic therapy in the interim
- Molecular panel on bone marrow does not need to be repeated if done within 3 months of starting AMG 427 therapy

7.2.2 Treatment

[figure not shown]
Treatment begins on day 1 (cycle 1 day 1) when the first dose of investigational product is administered to a subject.

After the mandatory hospitalization period (see Section 6.2.1.1), clinic visits may be conducted per institutional standard of care

The following procedures will be completed during the treatment period at the times designated in the Schedules of Assessments (Table 10 to Table 23).

Laboratory assessments that were done within 24 hours prior to treatment start do not need to be repeated at D1 prior to dose.

- Hospitalization (see Section 6.2.1.1 for minimum required hospitalization times)
- Investigational product doses (See Section 6.2.1.1 for details)
- Physical examination as per standard of care. Abnormal findings from the physical examination findings should be recorded in the events form.
- ECOG performance status
- Weight
- Vital signs (ie, blood pressure, heart rate, respiratory rate, and temperature)
- Pulse oximetry
- ECG triplicate measurement (1 set)
- Laboratory assessments: hematology, chemistry, coagulation, and urinalysis
- Biomarker assessments:

[figure not shown]

- AMG 427 PK sample collection
- [REDACTED]
- Bone marrow assessments
- Serious adverse event reporting
- Adverse event reporting
- Documentation of concomitant medications
- Contrast enhanced MRI or computed tomography (CT) scan (to be considered in case of CNS adverse event of grade ≥ 3 only, particularly in cases of confusion, disorientation or seizures)
- Receipt of protocol-required therapies (may include premedication)
- Pharmacogenetics sample (optional) collected pre-dose cycle 1 day 1
- For subjects to whom intra-subject dose escalation (see Section 7.2.2) applies:
 - ECG assessments should be performed as in cycle 1, regardless of actual study cycle
 - PK samples should be taken as in cycles 1 and 2, respectively, regardless of actual study cycle
 - All other assessments should be performed as per the schedule of assessments for the actual cycle.

7.2.3 End of Treatment Visit

The EOT visit will occur at the end of the last treatment cycle. For subjects who prematurely discontinue investigational product treatment, the EOT visit should occur as soon as possible after the last dose of investigational product was administered. The following procedures will be completed during the EOT visit as designated in the Schedules of Assessments (Table 10 to Table 23):

- Physical examination as per standard of care. Physical examination findings should be recorded on the appropriate eCRF.
- Vital signs (ie, blood pressure, heart rate, respiratory rate, and temperature)
- Pulse oximetry
- ECG triplicate measurement (1 set)
- Laboratory assessments: hematology, chemistry, coagulation, and urinalysis
- Biomarker assessments:

- AMG 427 PK sample collection

- Serious adverse event reporting
- Adverse event reporting
- Documentation of concomitant medications

[figure not shown]
7.2.4 Safety Follow-up Visit

The safety follow-up (SFU) visit is to be performed at least 4 weeks (or up to 7 days thereafter) after the last dose of AMG 427 or prior to the initiation of other AML therapy, whichever occurs earlier. **The safety follow-up period minimum is 30 days post last dose of investigational product.** All efforts should be made to conduct this visit including subjects who withdraw from treatment early. If it is not possible to conduct the SFU visit, documentation of the efforts to complete the visit should be provided in the source documents and noted as not done in the eCRF.

Subjects enrolled in the dose escalation phase who complete the safety follow-up visit will be considered to have completed the study.

The following procedures will be completed at the SFU visit as designated in the Schedules of Assessments ([Table 10](#) to [Table 23](#)).

- Physical examination as per standard of care. Physical examination findings should be recorded on the appropriate eCRF.
- ECOG Performance Status
- Weight
- Vital signs (ie, blood pressure, heart rate, respiratory rate, and temperature)
- Pulse oximetry
- ECG triplicate measurement (1 set)
- Laboratory assessments: hematology, chemistry, and coagulation
- Biomarker assessments:

- AMG 427 PK sample collection

- Serious adverse event reporting
- Adverse event reporting
- Documentation of concomitant medications
- Bone Marrow/MRD assessment

7.2.5 Long-term Follow-up

After the safety follow-up visit all subjects in the expansion phase only will enter the long-term follow-up (LTFU). Subjects will be contacted by telephone to assess survival, disease status, and anti-AML therapy following the end of AMG 427 treatment. On-site visits are not required by all subjects. Contact for all subjects will be attempted every 8 weeks (\pm 2 weeks) following the safety follow-up visit, as applicable, until death, subject withdraws full consent, or up to a maximum of 2 years from the first dose of AMG 427, whichever occurs first.

7.3 Description of Study Procedures

The sections below provide a description of the individual study procedures listed in Section [7.2](#).

7.3.1 Informed Consent

A signed ICF must be obtained from each subject prior to any study-mandated procedures.

7.3.2 Demographic Data

Demographic data collection including sex, age, race, and ethnicity will be collected in order to study their possible association with subject safety and treatment effectiveness. Additionally, demographic data will be used to study the impact of the protocol-required therapy on biomarker variability and PK.

7.3.3 Medical History and Prior Therapy

The investigator or designee will collect a complete medical and surgical history that started 5 years prior to screening up until the time of consent. Medical history will include information on the subject's concurrent medical conditions. Record all findings on the medical history eCRF.

Relevant medical history, including antecedent hematologic or oncologic disease, other diseases/symptoms such as fatigue, bleeding, and infection (resolved and ongoing) will be collected. AML history must date back to the initial diagnosis and any response duration must be recorded. The current toxicity grade will be collected for each condition that has not resolved. All prior cancer treatment therapies will be collected.

7.3.4 Concomitant Medications

Concomitant therapies (**including vaccines**) are to be collected from informed consent through the EOS. In case the screening period is shorter than 2 weeks (ie, informed consent is obtained less than 2 weeks prior to start of study treatment), concomitant

medications for which washout periods have to be observed (refer to Section 4.2, Section 6.3, and Section 6.9) are to be collected starting 2 weeks prior to start of study treatment. Collect therapy name, indication, dose, unit, frequency, route, start date, and stop date.

7.3.5 Physical Examination

A complete physical examination as per standard of care (rectal and vaginal examination not required) will be performed by the investigator or designee at screening and at the time points specified in the Schedules of Assessments (Table 10 to Table 23). The physical examination will include general appearance, including examination of the skin, spleen, and signs of extramedullary leukemia and respiratory, cardiovascular, musculoskeletal, and neurological systems.

The individual performing the physical examination will characterize their findings as either normal or abnormal. Abnormal physical examination findings found during screening should be reported on the Medical History eCRF. Abnormal physical examination findings found after the subject has provided consent will be reported on the Event eCRF.

7.3.6 ECOG Performance Status

Subjects will be graded according to the ECOG Performance Status (see Appendix F).

7.3.7 Height Measurements

Height in centimeters should be measured without shoes at screening.

7.3.8 Weight Measurements

Weight in kilograms should be measured without shoes.

7.3.9 Vital Signs

The following measurements must be performed: systolic/diastolic blood pressure, heart rate, respiratory rate, and temperature. Record all measurements on the vital signs eCRF.

The subject must be in a supine position in a rested and calm state for at least 5 minutes before blood pressure assessments are conducted. If the subject is unable to be in the supine position, the subject should be in most recumbent position as possible. The position selected for a subject should be the same that is used throughout the study and documented on the vital signs eCRF.

The location for temperature measurement selected for a subject should be the same that is used throughout the study and documented on the vital signs eCRF.

7.3.10 Pulse Oximetry

Oxygen saturation will be measured using a standard pulse oximeter. The subject must be in a rested and calm state for at least 5 minutes before pulse oximetry assessments are completed.

7.3.11 Electrocardiogram Performed in Triplicate

The subject must be in supine position in a rested and calm state for at least 5 minutes before ECG assessment is conducted. If the subject is unable to be in the supine position, the subject should be in most recumbent position as possible.

ECGs should be performed in a standardized method, in triplicate, (ie, approximately 30 seconds apart), prior to blood draws or other invasive procedures. Each ECG must include the following measurements: QRS, QT, QTc, RR, and PR intervals.

Electrocardiograms will be performed as follows:

- Baseline ECGs will be collected ≥ 30 minutes apart, with each baseline ECG in triplicate (ie, triplicate must be done approximately 30 seconds apart)
 - 2 sets collected at screening, and
 - 1 set collected pre-dose on cycle 1 day 1 [ie, total ≥ 9 ECGs])
- Triplicate ECGs at time points after dosing.

The investigator or designated site physician will review all ECGs. Electrocardiograms will be transferred electronically to an ECG central reader for processing per Amgen instructions. Once signed, the original ECG tracing will be retained with the subject's source documents. At the request of the sponsor, a copy of the original ECG will be made available to Amgen.

Standard ECG machines should be used for all study-related ECG requirements.

7.3.12 Clinical Laboratory Tests

The tests listed below in [Table 24](#) will be conducted on samples collected and analyzed by standard laboratory procedures at the time points specified in the Schedule of Assessments ([Table 10](#) to [Table 23](#)). The test results are to be recorded on the eCRFs. Missed test(s) that are not done must be reported as such on the eCRFs.

Additional procedures (eg, collection of an unscheduled blood sample to measure cytokine levels) deemed necessary as part of standard of care or as required by local laws and regulations may be performed at the investigator's discretion.

A serum pregnancy test will be performed locally at each site at the screening visit on all females unless they are surgically sterile or ≥ 2 years postmenopausal.

Table 24. List of Analytes

Local Laboratory					Central Laboratory
Chemistry	Hematology	Urinalysis	Coagulation	Other Labs	
Sodium	Hemoglobin	Specific gravity	PT	Pregnancy test ^a	[REDACTED]
Potassium	Hematocrit	pH	aPTT	Serology (HepB and HepC) ^b	AMG 427 PK samples
Bicarbonate or Total CO2	Platelets	Blood	INR	Bone marrow assessments ^{c,d}	Pharmacogenetics sample
Chloride	White Blood Cells	Protein	Fibrinogen	– morphology	[REDACTED]
Total protein	Total Neutrophils	Glucose	D-Dimer	– immunophenotype	[REDACTED]
Albumin	Segmented Neutrophils	Bilirubin	Antithrombin	– cytogenetics	[REDACTED]
Calcium	Lymphocytes	Ketones		– molecular panel	[REDACTED]
Magnesium	Monocytes	Microscopic exam		– MRD	[REDACTED]
Phosphorus	Bands/Stabs	(performed at the discretion of the investigator)			[REDACTED]
Glucose	Eosinophils				[REDACTED]
BUN or Urea	Basophils				[REDACTED]
Creatinine	Blasts				[REDACTED]
Total bilirubin	Absolute neutrophil count				[REDACTED]
ALP	Myeloblasts				[REDACTED]
AST	Erythrocyte sedimentation rate (ESR)				[REDACTED]
ALT	Ferritin				[REDACTED]
Amylase					[REDACTED]
Lipase					[REDACTED]
CRP					[REDACTED]
LDH					[REDACTED]
Uric Acid					[REDACTED]
eGFR (per institutional formula)					[REDACTED]

ALP = alkaline phosphatase; ALT = alanine aminotransferase; aPTT = activated partial thromboplastin time; AST = aspartate aminotransferase;; CRP = C-reactive protein; HepB = hepatitis B; HepC = hepatitis C; [REDACTED] INR = international normalize ratio; LDH = lactate dehydrogenase; [REDACTED]; MRD = Minimal/Measurable Residual Disease; PK = pharmacokinetic; PT = prothrombin time; [REDACTED]

^a Serum pregnancy test will be performed for all females unless surgically sterile or ≥ 2 years postmenopausal. Urine pregnancy test will be performed 4 weeks after the last dose of AMG 427 (if applicable).

^b Serology may include: HepBsAg (hepatitis B surface antigen) and HepCAb (hepatitis C antibody).

^c A screening molecular panel on bone marrow is required (NPM1, FLT3 ITD/TKD, IDH1/2, CEBPA, etc.). Molecular panel done within 3 months of study day 1 is acceptable.

^d Post-treatment bone marrow assessment is optional if the absolute peripheral blood blast count is ≥ 20% (screening bone marrow is still required).

7.3.13 Events

[figure not shown]
Adverse event and serious adverse event assessments will be made throughout the study and will be evaluated and recorded in the source documents and on the eCRF as specified in Sections 9.2 and 9.1.1, respectively. The severity of all events will be graded according to CTCAE, version 4.0 ([Appendix A](#)) unless specified otherwise. Exception: CRS will be graded according to the adopted grading system referenced in Lee et al, 2019 (see [Table 6](#)) and ICANS will be graded according to the criteria referenced in the publication by Lee et al, 2019 (see [Table 8](#)).

7.3.14 Head CT or Cranial MRI

A contrast-enhanced MRI or CT scan of the head should be considered for subjects who experienced a CNS event grade 2 or higher, particularly in cases of confusion, disorientation or seizures.

7.3.15 Pharmacokinetic Blood Sampling

Blood samples will be obtained for determination of serum concentrations of AMG 427 at the time points specified in the Schedules of Assessments ([Table 10](#) to [Table 23](#)). Blood must not be drawn from the port catheter during investigational product infusion and for at least 5 minutes after the end of infusion. End of infusion is defined as end of total infusion time (after investigational product and IV flush infusions). If a permanent central line with more than 1 lumen is used, blood draws can be done via the lumen that is not used for drug administration. However, the preference is for PK samples to be drawn peripherally during infusion. Sample collection, processing, storage, and shipping instructions are provided in a separate laboratory manual.

[figure not shown]

Table 25. Bone Marrow Collections

Test	Time point		
	Screening	D14 (for cohorts receiving D1, ± D3 & 5 doses)/D28 (for cohorts receiving D1, ± D3, 5, 8, 12, 19 doses) for all cycles	Unscheduled
Bone marrow aspirate	Required	Required (unless peripheral blood absolute blast count 20%, in which case bone marrow assessments are optional).	As needed (eg, if infusion-free period is prolonged beyond 4 weeks for cytopenia, bone marrow aspirate must be performed before starting next cycle of AMG 427)
Bone marrow biopsy	Required if aspirate is inadequate (eg, no spicules seen); optional if aspirate is adequate	Optional	Optional
Conventional cytogenetics	Required	Optional	Optional
Immunophenotype (including FLT3/CD135) ^a	Required on BM aspirate	Required on BM aspirate/peripheral blood blasts	Required on BM aspirates/peripheral blood blasts
Molecular panel (NPM1, FLT3 ITD/TKD, IDH1/2, CEBPA etc.)	Required on BM aspirate, within 3 months of day 1 is acceptable	Optional	Optional
Minimal/Measurable residual disease assessment		Required on BM aspirates only for subjects in CR	Required on BM aspirates only for subjects in CR
	Required for MRD+ AML subjects, only if not done within 3 months of enrollment (at local and central laboratory).		

AML = Acute Myeloid Leukemia; BM = bone marrow; C = cycle; CR = complete response;
 MRD = minimal/measurable residual disease; MRD+ = minimal/measurable residual disease-positive;
 R/R = relapsed/refractory; SOA = schedule of assessments
^a All disease/blast assessments must be confirmed by flow-cytometry based immunophenotype (a complete "AML flow panel" per institutional practices must be performed). This assessment may include FLT3 (CD135) expression (% and mean fluorescent intensity) on the myeloblasts.

[REDACTED]

Bone marrow assessments will be performed for the following:

- Morphology and immunophenotype to confirm eligibility at screening and response to treatment
- Standard cytogenetics – mandatory at screening only
- Immunological phenotyping to verify myeloid leukemia and assessments of MRD (if applicable) and [REDACTED]

• [REDACTED]

See Section 7.2.1 for guidelines for re-screening.

Additional bone marrow sampling may occur at other time points at the investigator's discretion as clinically indicated. Unscheduled bone marrow aspirate and biopsy results will be captured in the respective eCRFs.

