4.1 Inclusion Criteria

101. Subject has provided informed consent prior to initiation of any study-specific activities/procedures
102. Subjects ≥ 18 years of age at the time of signing consent
103. For R/R AML subjects only, AML as defined by the WHO Classification ([Appendix D](#)) as persisting or recurring following 1 or more treatment courses (exceptions noted in exclusion criteria). Subjects must have failed treatment with, be intolerant to, or must not be candidates for available therapies for the treatment of R/R AML (not applicable to MRD+ subjects)
104. For R/R AML subjects only, myeloblasts $\geq 5\%$ in bone marrow, as confirmed by immunophenotype by flow cytometry (not applicable to MRD+ subjects)
105. Eastern Cooperative Oncology Group (ECOG, [Appendix F](#)) Performance Status of ≤ 2
106. Renal function as follows:
 - serum creatinine < 2.0 mg/dL (176.84 $\mu\text{mol/L}$)
 - estimated glomerular filtration rate (eGFR) > 30 mL/min/1.73 m²
107. Hepatic function as follows:
 - aspartate aminotransferase (AST) and alanine aminotransferase (ALT) ≤ 3.0 x upper limit of normal (ULN)
 - bilirubin ≤ 1.5 x ULN (unless considered due to Gilbert's syndrome or hemolysis)
108. **(CLOSED)** Etanercept (Enbrel) substudy only:

No active tuberculosis in the setting of anti-TNF therapy

National guidelines should be followed for appropriate tuberculosis screening in the setting of anti-TNF therapy, including a minimum of:

 - Subject has a negative test for tuberculosis during screening defined as either:
 - Negative purified protein derivative (PPD) (< 5 mm induration at 48 to 72 hours after test is placed) OR
 - Negative Quantiferon test

Subjects with positive PPD and a history of bacillus Calmette-Guérin vaccination are allowed with a negative Quantiferon test.

Subjects with a positive PPD test (without a history of bacillus Calmette-Guérin vaccination) or subjects with a positive or indeterminate Quantiferon test are allowed if they have all of the following:

- no symptoms, per tuberculosis worksheet provided by Amgen
- documented history of a completed course of adequate treatment or prophylaxis (per local standard of care) prior to the start of investigational product
- no known exposure to a case of active tuberculosis after most recent prophylaxis
- no evidence of active tuberculosis on chest radiograph within 3 months prior to the first dose of investigational product

109. For the MRD+ Group, AML subjects in any CR/CRh/CRi:

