EOT = End of Treatment; MRD = minimal/measurable residual disease; MRD+ = minimal/measurable residual disease-positive

^a MRD+ groups will follow all Schedule C (Table 16 through Table 21) for all collections. Additionally, MRD+ cohorts will collect whole blood MRD at the following timepoints for all cycles.

Table 23. Schedule of Assessments: MRD+ Group Only – Whole Blood MRD Collection (Days 1, 3, 5, 8, 12, and 19)

MRD+ Whole Blood Collection (Day 1, 3, 5, 8, 12, and 19)				
Cycle	Cycle 1		Cycle ≥ 2	EOT
Week	1	4	4	
Cycle Day	1	28	28	
Hours	Pre-dose			
Whole blood MRD				
Whole blood MRD (MRD cohorts only) ^a	X ^a	X ^a	X ^a	X ^a

EOT = End of Treatment; MRD = minimal/measurable residual disease; MRD+ = minimal/measurable residual disease-positive

^a MRD+ cohorts will follow all Schedule C (Table 16 through Table 21) for all collections. Additionally, MRD+ cohorts will collect whole blood MRD at the following timepoints for all cycles.

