In this study, MRD assessments will be utilized as both an eligibility/inclusion criteria in the MRD+ cohort, as well as an additional efficacy endpoint for all cohorts. [REDACTED]

[figure not shown]
[REDACTED]. For subjects enrolling in MRD+ group, bone marrow sample for MRD assessment is required for both local and central testing (except at screening visit for subjects with historical test result available < 3 months from start of treatment).

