Appendix E. Revised International Working Group Response Criteria #

Category	Definition
Complete remission (CR) ¹	Bone marrow blasts < 5%; absence of blasts with Auer rods; absence of extramedullary disease; absolute neutrophil count > 1.0 x 10 ⁹ /L; platelet count > 100 x 10 ⁹ /L; independence of red cell transfusions
CR with incomplete recovery (CRi) ²	All CR criteria except for residual neutropenia (< 1.0 x 10 ⁹ /L) or thrombocytopenia (< 100 x 10 ⁹ /L)
Morphologic leukemia-free state ³	Bone marrow blasts < 5%; absence of blasts with Auer rods; absence of extramedullary disease; no hematologic recovery required
Partial remission	Relevant in the setting of phase 1 and 2 clinical trials only; all hematologic criteria of CR; decrease of bone marrow blast percentage to 5% to 25%; and decrease of pretreatment bone marrow blast percentage by at least 50%
Cytogenetic CR ⁴	Reversion to a normal karyotype at the time of morphologic CR (or CRi) in cases with an abnormal karyotype at the time of diagnosis; based on the evaluation of 20 metaphase cells from bone marrow
Molecular CR ⁵	No standard definition; depends on molecular target

Treatment Failure Criteria

Category	Definition
Resistant disease (RD)	Failure to achieve CR or CRi (general practice; phase 2/III trials), or failure to achieve CR, CRi, or PR (phase 1 trials); only includes patients surviving > 7 days following completion of initial treatment, with evidence of persistent leukemia by blood and/or bone marrow examination
Death in aplasia	Deaths occurring > 7 days following completion of initial treatment while cytopenic; with an aplastic or hypoplastic bone marrow obtained within 7 days of death, without evidence of persistent leukemia
Death from indeterminate cause	Deaths occurring before completion of therapy, or < 7 days following its completion; or deaths occurring > 7 days following completion of initial therapy with no blasts in the blood, but no bone marrow examination available Patients who do not complete the first course of therapy
Relapse ⁶	Bone marrow blasts > 5%; or reappearance of blasts in the blood; or development of extramedullary disease
Molecular or cytogenetic relapse	Reappearance of molecular or cytogenetic abnormality

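### Table 25 limits post-treatment marrow MRD to subjects in CR, in conflict with Section 7.5.2 and with MRD+ entry in CRh or CRi

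*Protocol*

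**What the plan says.** **Protocol Table 25 (bone marrow collections).** The aspirate at D14 or D28 of every cycle is "Required (unless peripheral blood absolute blast count 20%, in which case bone marrow assessments are optional"). The MRD row is narrower. In both the D14/D28 and the unscheduled columns it says "Required on BM aspirates only for subjects in CR". A second line in that row, whose column position is lost in the text available to us, says "Required for MRD+ AML subjects, only if not done within 3 months of enrollment (at local and central laboratory").

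**Protocol Section 4.1, criterion 109.** The entry condition is "For the MRD+ Group, AML subjects in any CR/CRh/CRi", with detectable MRD by local assessment.

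**Protocol Appendix E.** CRi is a category of its own: "All CR criteria except for residual neutropenia" or thrombocytopenia. CRh is also defined separately, with lower platelet and neutrophil limits than CR.

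**Protocol Section 7.5.2.** "For subjects enrolling in MRD+ group, bone marrow sample for MRD assessment is required for both local and central testing (except at screening visit" when a historical result less than 3 months old exists). Nothing in the visible text confines this to CR.

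**Use of the endpoint.** Protocol Section 10.1.1 defines response in MRD+ AML as conversion to MRD-. Protocol Section 10.3 and SAP Section 3.3 apply a futility rule to it. SAP Section 5 takes as denominator the subjects who are MRD+ at enrollment.

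**The concern.** Table 25 is where the marrow tests are tied to study days, so it is the natural source for a site's visit schedule. Read as written, it does not call for marrow MRD at D14/D28 in an MRD+ subject who is in CRh or CRi, although such subjects are eligible and Section 7.5.2 expects the test.

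CRh and CRi differ from CR mainly in blood counts, and the protocol lists cytopenia as an important potential risk (Section 2.3, Table 2). It is therefore foreseeable that some MRD+ subjects will not meet full CR criteria at a scheduled marrow. The documents do not say how many.

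What is at stake is ascertainment of conversion, the response endpoint of the 50-subject MRD+ expansion and the count on which its futility looks depend. A subject without a post-treatment marrow MRD result cannot be shown to have converted.

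**Working it through.** **Step 1: the passages side by side**

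| Question | Table 25 | Rest of the protocol |
|---|---|---|
| Is a marrow aspirate taken at D14/D28? | Yes, every cycle, optional only at the blast threshold | Consistent (Table 24, footnote d) |
| Who has post-treatment marrow MRD? | Subjects in CR | The MRD+ group, local and central, except at screening with a recent result (Section 7.5.2) |
| Which states can an MRD+ subject be in at entry? | Not stated | CR, CRh or CRi (criterion 109) |
| Does CR include CRh and CRi? | The abbreviation key gives only complete response | Defined apart (Appendix E) and listed separately among the R/R responses (Section 10.1.1) |

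The second line of the MRD row refers to enrollment and a 3-month window, so it reads as a screening rule. It sets no D14/D28 requirement. The two rules therefore differ for MRD+ subjects in CRh or CRi.

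**Step 2: reproduce the plan's futility figures**

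Inputs, from protocol Section 10.3: stop if there are at most 2 responders in 12, 4 in 18 or 5 in 24; otherwise continue to 50. With S_n the number of responders among the first n subjects,

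P(stop) = P(S_12 ≤ 2) + P(S_12 > 2, S_18 ≤ 4) + P(S_12 > 2, S_18 > 4, S_24 ≤ 5).

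At a true rate p = 0.35:

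- First look: 0.65^12 + 12(0.35)(0.65^11) + 66(0.35^2)(0.65^10) = 0.0057 + 0.0368 + 0.1088 = 0.1513.
- The exact binomial recursion adds 0.0802 at the second look and 0.0103 at the third. The cumulative values are 0.1513, 0.2315 and 0.2418.
- Average sample size: 12(0.1513) + 18(0.0802) + 24(0.0103) + 50(1 − 0.2418) = 41.4.

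Protocol Table 29 (SAP Table 4) gives 0.15, 0.23, 0.24 and 41.4. The other four rows also reproduce, with probabilities within 0.01 and average sample sizes within 0.2. No figure in the plan is in dispute, and the fix changes none.

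**Step 3: illustration of untested subjects**

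Let f be the share of MRD+ subjects never tested. Assume that they would convert at the same true rate and are counted as non-converters. The observed rate is then p(1 − f). With p = 0.35:

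| f (assumed) | Observed rate | P(stop by 24) |
|---|---|---|
| 0 | 0.350 | 0.242 |
| 10% | 0.35 × 0.90 = 0.315 | 0.348 |
| 20% | 0.35 × 0.80 = 0.280 | 0.475 |
| 30% | 0.35 × 0.70 = 0.245 | 0.612 |

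If untested subjects were instead left out of the denominator, the cost would be precision. At 40% conversion the exact 80% CI is 30.6% to 50.1% for 20/50 (the plan's figure) and 28.7% to 52.3% for 14/35, which is f = 30%.

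**The case against.** The strongest reply is that the protocol already requires the test. Section 7.5.2 covers the whole MRD+ group, with screening the only exception, and the aspirate is mandatory. This stands, and it limits the point to an inconsistency between two passages. A reader might infer that the design leaves conversion unmeasured in CRh and CRi subjects. The documents do not support that, because a site following Section 7.5.2 would test them.

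Other collections exist. Tables 22 and 23 add whole blood MRD for the MRD+ group at D14 or D28 of every cycle and at end of treatment ("MRD+ cohorts will collect whole blood MRD at the following timepoints for all cycles"). Section 7.2.4 lists a marrow/MRD assessment at safety follow-up. Flow immunophenotyping is required on each D14/D28 aspirate. These reduce the risk, but no visible text says that blood MRD or the routine panel defines conversion, and the follow-up marrow comes only once.

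The row may be damaged. One line has lost its column, and a group label may have gone with it, so the CR limit may have been meant for R/R subjects. CR may also have been meant loosely. Neither can be settled from the text, and either would be resolved by clearer wording.

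The efficacy summary in Section 2.2.4 reports an R/R subject in CRi who was MRD-negative by flow. That shows a CRi subject was tested, and it is no evidence that such subjects are missed.

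Finally, a reader might infer that untested subjects count as failures. The visible SAP does not say so. The conversion definition in SAP Section 5 is followed by redacted text, and the missing-data rules in SAP Section 8.3 do not mention MRD response.

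**Conclusion.** The conflict is real, and it bears on the endpoint behind the MRD+ futility decision. Table 25 limits D14/D28 and unscheduled marrow MRD to CR. Section 7.5.2 does not, and criterion 109 admits CRh and CRi. The supportable consequence is conditional: a site working from Table 25 alone could omit the test in CRh or CRi subjects, and conversion would be unmeasured for them at those visits.

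The size is not known. The stop probabilities of 0.35 and 0.61, against 0.24 at a true rate of 35%, rest on an assumed 10% or 30% untested share, on no test at any visit, and on scoring those subjects as non-converters. The documents supply neither the share nor, in visible text, the scoring rule. The figures show how sensitive the rule is to missed conversions and do not predict what will happen.

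It might also be inferred that R/R subjects in CRh or CRi must have marrow MRD. Section 7.5.2 calls MRD an additional efficacy endpoint for all cohorts, but its visible sampling requirement names only the MRD+ group. Testing those R/R subjects is optional.

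**What to change.** Align the Table 25 MRD row with Section 7.5.2: marrow MRD is required at each D14/D28 aspirate for all MRD+ group subjects, whether in CR, CRh or CRi. Label the screening line as such, and bring the unscheduled column into line in the same edit. Whether to extend testing to R/R subjects in CRh or CRi is the sponsor's choice.

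Unless the redacted text already does so, the SAP should also state how an MRD+ subject with no post-treatment MRD result is handled in the conversion rate and at the futility looks.

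The cost is table wording and one SAP sentence. The aspirate is already required, and Section 7.5.2 already calls for the test, so no procedure is added for the subject. Table 29 and the planned confidence intervals stay as they are.
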